7.7. Lost to Follow up

A patient will be considered lost to follow-up if he or she repeatedly fails to return for scheduled visits and is unable to be contacted by the study site.

The following actions must be taken if a patient fails to return to the clinic for a required study visit:

- The site must attempt to contact the patient or the patient's family and reschedule the missed visit as soon as possible and counsel the patient on the importance of maintaining the assigned visit schedule and ascertain whether the patient wishes to and/or should continue in the trial.
- Before a patient is deemed lost to follow up, the investigator or designee must make every effort to regain contact with the patient or the patient's family (where possible, 3 telephone calls and, if necessary, a certified letter to the patient's last known mailing address or local equivalent methods). These contact attempts should be documented in the patient's medical record.
- Should the patient continue to be unreachable, he/she will be considered to have discontinued from the trial and are lost to follow-up.

Closing of specific sites or discontinuation of the trial are handled as part of Appendix 1 ([Section 10.1.7](#)).

8. STUDY ASSESSMENTS AND PROCEDURES

There will be up to six clinic visits, two remote lab visits, and eight remote visits (that requires a phone or video call), with windows to aid in scheduling as shown in [Table 3](#). If a patient visit must be scheduled outside the visit window, the Medical Monitor should be contacted. If a patient is scheduled for an in-clinic visit outside the visit window, the ALSFRS-R should be obtained by phone or video call during the visit window when possible, while the other visit related procedures will be obtained outside of the visit window when the patient is seen in clinic. Day 1 anchors all subsequent study visits.

Table 3: CY 5032 Visit Windows

Visit	Visit Window
Start of Dosing (Day 1): clinic visit	
End of Week 4: remote visit	28 days \pm 4 days
End of Week 6: remote lab visit	42 days \pm 4 days
End of Week 8: remote visit	56 days \pm 4 days
End of Week 12: clinic visit	84 days \pm 4 days
End of Week 16: remote visit	112 days \pm 4 days
End of Week 18: remote lab visit	126 days \pm 4 days
End of Week 20: remote visit	140 days \pm 4 days
End of Week 24: clinic visit	168 days \pm 4 days
End of Week 28: remote visit	196 days \pm 4 days
End of Week 32: remote visit	224 days \pm 4 days
End of Week 36: clinic visit	252 days \pm 4 days
End of Week 40: remote visit	280 days \pm 4 days
End of Week 44: remote visit	308 days \pm 4 days
End of Week 48: clinic visit	336 days \pm 4 days
FU: End of Week 52: clinic visit	364 days \pm 4 days

Study procedures and their timing are summarized in the SoA ([Section 1.3](#)). If Day 1 in CY 5032 occurs more than 6-weeks after completion of the FU Visit (Week 52) in CY 5031, the initial dose of study drug will not be taken by the patient until their safety lab results are available and the $eGFR_{CysC} \geq 45 \text{ ml/min/1.73m}^2$ and $eGFR_{Cr} \geq 45 \text{ ml/min/1.73m}^2$, $ALT/AST < 3 \times ULN$, and bilirubin is normal or if abnormal reported as non-clinically significant by the investigator.

Prospective approval of a protocol deviation to recruitment and enrollment criteria, also known as a protocol waiver or exception, is not permitted.

Immediate safety concerns should be discussed with the Medical Monitor immediately upon occurrence or awareness to determine if the patient should continue or discontinue study drug.

Adherence to the trial design requirements, including those specified in the SoA ([Section 1.3](#)), is essential and required for trial conduct.

Repeat or unscheduled samples may be taken for safety reasons or for technical issues with the samples.

Remote lab visits at Week 6 and Week 18 may occur in-clinic or by another method approved by the Sponsor if arrangements cannot be made for the home health vendor to draw lab samples at the patient's home.

If scheduled in-clinic visits are not possible, remote visits will be made and documented to review trial assessments, safety, adverse events, provide safety laboratory samples, and concomitant medications as detailed in the Study Manual (see [Section 4.1](#), Overall Study Design for additional details on converting in-clinic visits to remote visits).

8.1. Efficacy Assessments

The sequence of all trial related procedures including the relationship of procedures relative to dosing should be followed as detailed in the Study Manual.

8.1.1. ALSFRS-R

The ALSFRS-R will be performed at each study visit (both in-clinic and remote) as described in the Study Manual.

8.1.2. Health Economic Outcomes Measures

During the course of the trial, if the patient is prescribed and agrees to obtain, and/or receives any of the following durable medical equipment (DME), reason for obtaining, timing and extent of use will be recorded as described in the Study Manual:

- Non-invasive ventilation (including type of device)
- Gastrostomy tube
- Manual wheelchair
- Power wheelchair
- Augmentative and alternative communication (including type of device)

Obtaining information about the DME use should be obtained at every in-clinic and remote visit.

8.1.3. Hospitalizations

Hospitalizations experienced by a patient following enrollment in CY 5032 and occurring in the context of a serious adverse event will be determined by the Investigator as being either related to ALS, unrelated to ALS, or indeterminate. Hospitalizations deemed related to ALS cover those that are both related to disease progression, hospitalizations that may occur to address an ongoing ALS symptom or to be preventative (such as hospitalization for a PEG / radiologically inserted percutaneous gastronomy (RIG) tube), as well as those to address a complication of a treatment being received for ALS. This information will be recorded and entered into the electronic data capture (EDC) system. Hospitalizations that are for social reasons, or those that

were planned are not considered SAEs and therefore relationship to ALS will not be recorded. Further details are described in the Study Manual.

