8.3.1.2. Definition of Serious Adverse Event

A SAE is defined as any untoward medical occurrence that at any dose:

- Results in death
- Is life threatening, NOTE: The term "life-threatening" in the definition of "serious" refers to an event in which the patient was at risk of death at the time of the event; it does not refer to an event which hypothetically might have caused death if it were more severe
- Requires inpatient hospitalization or prolongation of existing hospitalization
- Results in persistent or significant disability/incapacity, or

- Is a congenital anomaly/birth defect
- Is an important medical event

Medical and scientific judgement should be exercised in deciding whether expedited reporting is appropriate in other situations, such as important medical events that may not be immediately life-threatening or result in death or hospitalization but may jeopardize the patient or may require intervention to prevent one of the other outcomes listed in the definition above. These should also usually be considered serious. Examples of such events include invasive or malignant cancers; intensive treatment in an emergency room or at home for allergic bronchospasm; blood dyscrasias or convulsions that do not result in hospitalization; or development of drug dependency or drug abuse.

An adverse event would meet the criterion of “requires hospitalization,” if the event necessitated an admission to a health care facility (eg, overnight stay).

The following reasons for hospitalization are exempted from being reported:

- Hospitalization for cosmetic elective surgery, or social and/or convenience reasons.
- Hospitalization for pre-planned (ie, planned prior to signing informed consent) surgery or standard monitoring of a pre-existing disease or medical condition that did not worsen, eg, hospitalization for coronary angiography in a patient with stable angina pectoris.

However, complications that occur during an exempted hospitalization are AEs or SAEs (for example if a complication prolongs a pre-planned hospitalization).

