8.3.1.7. Reporting of AEs

The investigator is responsible for ensuring that all adverse events observed by the investigator or reported by the patient that occur after starting the study drug through end of study are recorded in the AE CRF.

ALS is a progressive and uniformly fatal neurodegenerative disorder associated with relentlessly progressive loss of motor function, including appendicular, craniobulbar, and respiratory function due to the degeneration of the upper and lower motor neurons which control and innervate the voluntary skeletal muscles. The following conditions are anticipated to occur in the study population as signs/symptoms of ALS progression and do not need to be recorded as an AE unless they meet the criteria for an SAE, are felt to be related to the study drug, or they are occurring outside what is expected for the normal course of the disease ([Brown 2017](#)).

Table 4: Signs and Symptoms Commonly Associated with ALS

MedDRA Preferred Term ^a	MedDRA Preferred Term ^a
Dysarthria	Muscle spasticity
Dysphagia	Muscle contractions involuntary
Dyspnoea	Muscle spasms
Gait disturbance	Muscular weakness

^aMedDRA Version 23.0

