8.2. Adverse Events

8.2.1. Summaries of Adverse Event Incidence Rates for All Subjects

Adverse events (AEs) will be coded by System Organ Class (SOC) and Preferred Term (PT) using the Medical Dictionary for Regulatory Activities (MedDRA) version 26.0.

Analyses of AEs will be performed for those events that are considered treatment emergent AEs (TEAEs), where treatment emergence is defined as any adverse events with an onset after initiation of study drug dosing in CY 5032, or an AE present at initiation of study drug dosing that worsens in severity after initiation of study drug dosing. If an AE had the onset in the preceding study CY 5031 and carry over to the open-label extension, it will not be considered as treatment emergent in CY 5032 data.

The following summaries of AEs and serious AEs (SAEs) will be presented by overall:

- TEAEs by SOC and PT
- TEAEs by PT
- TEAEs by SOC, PT and Severity (Grade 1-5)
- TEAEs related to study drug by SOC and PT

- TEAEs related to study drug by PT
- TESAEs by SOC and PT
- TESAEs by PT
- TESAEs related to study drug by PT
- TEAEs leading to drug discontinuation by PT
- TEAEs leading to death

AE summaries will be presented by descending order of PT in the overall column, and if applicable, SOC will be ordered first, with PT sorted within the SOC.

A patient will be counted only once within each SOC and PT. For the summary of AEs by severity, patients will be counted only once within each primary SOC/preferred term and will only be counted under the maximum severity.

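### Protocol 8.1.3 takes every planned hospitalization out of SAE status, but the SAE definition in 8.3.1.2 exempts planned admissions only if they were planned before consent

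*Protocol*

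**What the plan says.** Protocol 8.1.3 (Hospitalizations) asks the investigator to classify, by relationship to ALS, hospitalizations that follow CY 5032 enrollment and are "occurring in the context of a serious adverse event". Among those deemed related to ALS it includes admissions meant "to be preventative (such as hospitalization for a PEG / radiologically inserted percutaneous gastronomy (RIG) tube". The section then says that hospitalizations for social reasons, or those that "were planned are not considered SAEs and therefore relationship to ALS will not be recorded". It refers to the Study Manual for further detail and does not mention 8.3.1.2.

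Protocol 8.3.1.2 (Definition of Serious Adverse Event) lists as an SAE criterion: "Requires inpatient hospitalization or prolongation of existing hospitalization". It has two exemptions. One is "Hospitalization for cosmetic elective surgery, or social and/or convenience reasons". The other is "Hospitalization for pre-planned (ie, planned prior to signing informed consent) surgery or standard monitoring of a pre-existing disease" or medical condition, with the qualifier that it has not worsened.

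Protocol 8.3.1.7 says that the ALS signs in Table 4, which include dysphagia, "do not need to be recorded as an AE unless they meet the criteria for an SAE", are thought to be drug-related, or fall outside the expected course of the disease. Protocol 8.3.1.8 requires SAEs to reach the sponsor within 12 hours of the investigator's knowledge.

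The abbreviated SAP keeps serious events. Section 8.1 counts patients with serious TEAEs, and Section 8.2.1 lists "TESAEs by SOC and PT".

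**The concern.** Two current sections of the protocol answer the same question differently: is an admission that was arranged during the extension an SAE? Gastrostomy placement is the protocol's own example, and 8.1.2 lists the gastrostomy tube among the equipment to be tracked, so the case is one the plan itself foresees.

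Three things depend on the answer:

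- whether the 12-hour reporting duty applies;
- whether the event enters the serious-event summaries;
- for an expected Table 4 sign not attributed to study drug, whether any AE is recorded. The primary endpoint is AE incidence, so this last effect reaches it directly.

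If sites read the protocol differently, these counts partly reflect the section each site followed.

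**Working it through.** No arithmetic applies. The check sets the rules side by side and runs test admissions through them.

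**Test case.** A patient's swallowing worsens after the first CY 5032 dose. The investigator judges this expected for ALS and unrelated to study drug. An inpatient gastrostomy admission is then booked, after CY 5032 consent.

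| Rule | Reasoning | Result |
|---|---|---|
| 8.3.1.2 | The event leads to inpatient admission. It was not planned before consent, and it is not cosmetic, social or for convenience, so no exemption applies. | SAE |
| 8.1.3, planned-admission wording | The admission was planned, and no time limit is stated. | Not an SAE; ALS relationship not recorded |
| 8.1.3, preventive PEG/RIG example | Tube placement is named as an ALS-related hospitalization within a group defined by its link to an SAE. | SAE-linked; ALS relationship recorded |

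The second row contradicts the first, and it contradicts the third within one section.

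**The qualifier about worsening.** In 8.3.1.2 the words on a condition that has not worsened could attach to standard monitoring only, or to surgery as well. The test case does not depend on this, because it already fails the consent-date condition.

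**Where the rules agree.** For surgery planned before consent for a stable condition, both sections give non-SAE. For a purely social admission, both give non-SAE. An unplanned tube placement fits both parts of 8.1.3. The conflict is confined to admissions planned after consent, or planned for a condition that then worsened.

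**What follows in the test case.**

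1. *Reporting.* Under 8.3.1.2 the 12-hour rule in 8.3.1.8 applies. Under 8.1.3 it does not.
2. *AE recording.* Dysphagia is in Table 4. Expected and unrelated, it must be recorded under 8.3.1.7 only if it meets an SAE criterion. A site that follows 8.1.3 may therefore record no AE at all, rather than a non-serious one.
3. *Summaries.* If the event counts as treatment-emergent under SAP 8.2.1, it appears among the serious TEAEs on one reading and not on the other. SAP Section 9 narrows the tables to an overview of AEs, among other items, but the overall summary in SAP 8.1 still includes a serious-event count.

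**The case against.** The strongest reply is that the sections can be read together. Section 8.1.3 is an efficacy-assessment section, while 8.3.1.2 is the titled SAE definition. The pair in 8.1.3, social or planned, resembles the exemptions in 8.3.1.2, so planned may be shorthand for pre-planned. That reading also saves the preventive PEG/RIG example, which would lose much of its content if every arranged admission were excluded. The Study Manual, which is not among the documents, may say this. The reading is sensible and is probably what was intended. But 8.1.3 neither states it nor refers to the definition, and a manual should not have to correct protocol text. The reply lowers confidence that sites actually diverged; it does not remove the conflict.

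A second reply is that a purely prophylactic tube placement, with nothing having worsened, may involve no untoward event and so no SAE on either reading. That stands, and it is why the test case involves worsening swallowing.

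A reader might go further and infer that planned admissions drop out of the hospitalization endpoints. The documents do not establish this. Section 8.1.3 withholds only the ALS-relationship field for such admissions. The Schedule of Activities collects hospitalizations with no SAE condition, and the endpoints are not limited to SAE-linked or ALS-related admissions. SAP Sections 7 and 9 also reduce efficacy to a descriptive ALSFRS-R summary and drop formal analyses, so the question is largely moot.

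A reader might also apply a guessed gastrostomy rate to the roughly 400 anticipated patients. The documents give no such rate, and SAP 4.2 says the study was terminated early, so neither that enrollment nor full follow-up can be assumed.

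**Conclusion.** The contradiction holds. An admission arranged after CY 5032 consent for a worsening condition is an SAE under Protocol 8.3.1.2 and not an SAE under 8.1.3, and 8.1.3 is inconsistent with its own preventive PEG/RIG example when that admission is planned. The effect falls on expedited reporting, on the serious TEAE summaries kept in the abbreviated SAP, and on whether expected, unrelated Table 4 signs are recorded as AEs.

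The size cannot be estimated from the documents. It depends on how many such admissions occurred, how many of those patients had another SAE, and which section each site followed. Sites that followed 8.1.3 literally would under-report relative to the SAE definition. The remaining analyses are descriptive and presented overall, so no between-group comparison or test is at stake. The conclusion rests on the protocol text as it stands and assumes only that the Study Manual does not formally override it.

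**What to change.** Reconcile the two sections so that one rule governs. In Protocol 8.1.3, replace the wording on planned admissions with a cross-reference to the exemptions in 8.3.1.2, and inform the sites.

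Since the trial has been stopped, the data step matters more than the wording. Before lock, query the admissions that sites classed as planned, reclassify them under that single rule, and check that any associated Table 4 sign was recorded where the rule requires it. If the database is already locked, state in the study report which rule was applied to planned admissions.

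The cost is one sentence, a site clarification and a short data query. The reported SAE count may rise slightly.

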8.2. Safety Assessments

Planned time points for all safety assessments are provided in the SoA ([Section 1.3](#)).

8.2.1. Physical Examinations

A routine physical examination will be performed on Day 1 if the patient enrolls in the OLE on the same day as the Week 48 visit in CY 5031. If a patient enrolls in the OLE at the follow-up visit in CY 5031, a physical exam does not need to be repeated on Day 1 of the OLE.

An abbreviated physical examination (consisting of an examination of general appearance, skin, lungs, cardiovascular and abdomen) will be performed at the Week 52 visit.

8.2.2. Vital Signs

Heart rate, blood pressure, and respiratory rate (measured after the patient has been resting and seated for at least 3 minutes), will be obtained at all in-clinic study visits. Temperature will also be obtained at the Day 1 visit. Height that was recorded in CY 5031 can be used to calculate the body mass index (BMI). If the pulse is <50 or >100 bpm, mean systolic blood pressure <90 or >160 mm Hg; mean diastolic blood pressure <50 or >100 mm Hg or the respiratory rate is <10 or >20 breaths per minute, the out-of-range vital sign should be re-checked following the patient resting for 10 minutes in the seated position. If the in-clinic visit is converted to a remote visit, vital signs will not be performed.

8.2.3. Neurological Examinations

A brief neurological exam will include assessments of specific cranial nerves (eye, face, and tongue movements), motor strength in specific muscles, evaluation of deep tendon and bilateral plantar reflexes, sensory testing, and tests of co-ordination (limited to finger-to-nose and heel-to-shin when possible to assess). This will be administered on Day 1 if the patient enrolls in the OLE on the same day as the Week 48 visit in CY 5031. If a patient enrolls in the OLE at the follow-up visit in CY 5031, a neurological exam does not need to be repeated on Day 1 of the OLE. It will also be performed at the Week 52 visit as described in the Study Manual.

8.2.4. Laboratory Assessments

See Appendix 2 ([Section 10.2](#)) for the list of clinical laboratory tests to be performed and see the SoA ([Section 1.3](#)) for the timing and frequency.

The investigator must review the laboratory report, document this review, and record any clinically relevant changes occurring during the trial in the AE section of the CRF. Clinically significant abnormal laboratory findings are those which are not associated with the underlying disease; if the abnormal laboratory finding is felt to be associated with the underlying disease but is judged by the investigator to be more severe than expected for the patient's condition it should be recorded as such.

All protocol-required laboratory assessments, as defined in Appendix 2 ([Section 10.2](#)), must be conducted in accordance with the laboratory manual and the SoA ([Section 1.3](#)).

8.3. Adverse Events and Serious Adverse Events

8.3.1. Adverse Events

8.3.1.1. Definition of Adverse Event

An AE is defined as any untoward medical occurrence in a patient or clinical investigation patient administered a pharmaceutical product and which does not necessarily have a causal relationship with this treatment. An AE can therefore be any unfavorable and unintended sign (including an abnormal laboratory finding), symptom, or disease temporally associated with the use of study drug, whether or not related to study drug.

Adverse events include:

- Exacerbation of a chronic or intermittent pre-existing condition (a condition that occurred before the patient was exposed to reldesemtiv) including either an increase in frequency and/or intensity of the condition.
- New conditions detected or diagnosed after IP administration even though it may have been present before the start of the trial.
- Abnormal assessments, eg, change on physical examination, electrocardiogram (ECG) findings, if they represent a clinically significant finding that was not present at trial start or worsened during the course of the trial.
- Laboratory test abnormalities if they represent a clinically significant finding, symptomatic or not, which was not present at trial start or worsened during the course of the trial, require treatment, or led to dose reduction, interruption or permanent discontinuation of IP. In general, abnormal laboratory findings without clinical significance (based on the investigator's judgment) are not to be recorded as adverse events. Where applicable, clinical sequelae (not the laboratory abnormality) are to be recorded as the adverse event.
- Signs, symptoms, or the clinical sequelae of a suspected drug-drug interaction.
- Signs, symptoms, or the clinical sequelae of a suspected overdose of either study drug or a concomitant medication. Overdose per se will not be reported as an AE/SAE unless it is an intentional overdose taken with possible suicidal/self-harming intent. Such overdoses should be reported regardless of sequelae.

